11.5. Cohorts for Analyses

11.5.1. Total vaccinated cohort

The total vaccinated cohort (TVC) will include all subjects with at least one study vaccine administration documented.

A safety analysis based on the TVC will include all vaccinated subjects.

An immunogenicity analysis based on the TVC will include all vaccinated subjects for whom immunogenicity data are available.

The TVC analysis will be performed per treatment actually administered at Dose 1.

11.5.2. According-to-protocol cohort for analysis of immunogenicity

The ATP cohort for analysis of immunogenicity will be defined by timepoint and will consist of all subjects from the TVC who complied with eligibility criteria, study procedures up to the end of the study and had immunogenicity results in the epoch as described below.

More specifically, the ATP cohort for analysis of immunogenicity up to Visit 9 (Day 60)/at Visit 10 (Day 365) will include all evaluable subjects:

- Who met all eligibility criteria (i.e. no protocol violation linked to the inclusion/exclusion criteria, including age).

- Who received at least one dose of study vaccine.
- For whom the administration route and site of the vaccine was as according to protocol.
- Who received the vaccine according to protocol procedures.
- Who complied with the vaccination schedule, as specified in [Table 5](#).
- Who did not receive a concomitant medication/product leading to exclusion from an ATP analysis, as described in Section [7.6.2](#), up to Visit 9 (Day 60)/up to Visit 10 (Day 365).
- Who complied with the timings of the post vaccination blood sampling for immune response evaluation, up to Visit 9 (Day 60) /at Visit 10 (Day 365), as specified in [Table 5](#).
- For whom post-vaccination immunogenicity results are available for at least one assay up to Visit 9 (Day 60) /at Visit 10 (Day 365).

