1.1.6. Pre-clinical and clinical experience

The candidate vaccine is based on the RSV viral proteins F, N and M2-1 encoded by a chimpanzee-derived adenovector (ChAd155-RSV). A number of pre-clinical studies were conducted and have demonstrated immunogenicity, efficacy and safety of intramuscular (IM) injection of the ChAd155-RSV vaccine. Several animal models have been selected for such studies: mice, cotton rats and newborn calves. Importantly, vaccination has not induced hallmarks of enhanced pathology in these models.

The immunogenicity, safety and reactogenicity of the pediatric candidate RSV vaccine (ChAd155-RSV vaccine) have been evaluated in healthy adults aged 18 to 45 years (study 201974 [RSV PED-001; NCT02491463]) There were no significant safety concerns identified up to Day 60 in study RSV PED-001. Overall, the ChAd155-RSV vaccine high dose (Hd) (5×10^{10} vp) seems to be more reactogenic (local and general) than the ChAd155-RSV vaccine low dose (Ld) (5×10^9 vp), however, the reactogenicity profile was less than that observed in the Bexsero group. No safety signal from the assessed hematology parameters (hemoglobin, platelet count, prothrombin time and APTT) was observed in subjects receiving the ChAd155-RSV vaccine. No significant reductions in platelet count or clinically significant changes in coagulation parameters were observed up to 30 days post Dose 2. An approximately 2.4-fold increase in RSV-A neutralizing antibody titers (geometric mean titer [GMT] from baseline) was observed in both RSV-Ld and RSV-Hd after Dose 1. No booster effect was evident after Dose 2. An anti-F IgA and IgG antibody secreting B-cells response and an RSV F, N and M2-1 specific IFN- γ secreting T-cells response in RSV-Hd group after the first dose were observed with ELISpot. There was no booster response after the second vaccination. There was no specific vaccine-induced CD4 T-cellular response observed with intracellular staining (ICS). For CD8 T-cells only a weak CD8 IFN- γ response to N was shown with ICS for some subjects.

Please refer to the current IB for information regarding the pre-clinical and clinical studies of GlaxoSmithKline (GSK) Biologicals' investigational ChAd155-RSV vaccine.

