11.2. Secondary endpoints

- Occurrence of SAEs from study start (Day 0) up to study conclusion (Day 730).
- Occurrence of RSV-LRTI (AE of specific interest) as from Dose 1 administration up to study conclusion (Day 730).
- Occurrence of RSV-RTI, RSV-LRTI, severe RSV-LRTI (according to standardized case definitions) as from Dose 1 administration up to study conclusion (Day 730).
- Magnitude of the CMI response to the investigational RSV vaccine, pre-vaccination (Screening), post-Dose 1 (Day 30) and post-Dose 2 (Day 60 and Day 365).
 - CD3+/CD4+ T-cells expressing at least two markers among CD40L, IL-2, TNF- α , and IFN- γ upon stimulation with F, N and M2-1 peptide pools.

- Humoral response to the investigational RSV vaccine, pre-vaccination (Screening), post-Dose 1 (Day 30) and post-Dose 2 (Day 60 and Day 365):
 - Neutralizing antibody titers against RSV-A.
 - RSV F antibody concentrations.
- Humoral response to the investigational RSV vaccine, pre-vaccination (Screening), post-Dose 1 (Day 30) and post-Dose 2 (Day 60):
 - Palivizumab-competing antibody concentrations.

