#### 5.1.2. According-to-protocol cohort for analysis of immunogenicity

The ATP cohort for analysis of immunogenicity will be defined by timepoint and will consist of all subjects from the TVC who complied with eligibility criteria, study procedures up to the end of the study and had immunogenicity results in the epoch as described below.

More specifically, the ATP cohort for analysis of immunogenicity up to Visit 9 (Day 61)/at Visit 10 (Day 366) will include all evaluable subjects:

- Who met all eligibility criteria (i.e. no protocol violation linked to the inclusion/exclusion criteria, including age).
- Who received two dose of study vaccine.
- For whom the administration route and site of the vaccine was as according to protocol.

- Who received the vaccine according to protocol procedures.
- Who complied with the vaccination schedule, as specified in Table 5 of the protocol.
- Who did not receive a concomitant medication/product leading to exclusion from an ATP analysis, as described in Section 7.6.2 of the protocol, up to Visit 9 (Day 61)/up to Visit 10 (Day 366).
- Who complied with the timings of the post vaccination blood sampling for immune response evaluation, up to Visit 9 (Day 61) /at Visit 10 (Day 366), as specified in Table 5 of the protocol.
- For whom post-vaccination immunogenicity results are available for at least one assay up to Visit 9 (Day 61) /at Visit 10 (Day 366).

Note that in order to align to ICH and cDISC terminology the Total Vaccinated Cohort and the According to Protocol cohort have been renamed Exposed Set (ES) and Per-Protocol Set (PPS) respectively.

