**5.2.2. Elimination from Per-protocol analysis Set (PPS)**

**5.2.2.1. Excluded subjects**

A subject will be excluded from the PPS for analysis of immunogenicity at Day 61 and Day 366 under the following conditions

Code	Condition under which the code is used
900	Invalid informed consent or fraud data ( Subjects receiving a code 900 should not receive any other elimination codes )
1030	Study vaccine not administered at all ( Subjects receiving a code 1030 should not receive any other elimination codes )
1050	Randomization failure
1070\$	Subjects got vaccinated with the correct vaccine but containing a lower volume
1070\$	Administration not according to protocol for reason specified by the investigator, other than side, site and route
1070\$	Site or route of study vaccine administration wrong or unknown
1070\$	Wrong replacement or study vaccine administered (not compatible with the vaccine regimen associated to the treatment number)
1070\$	Administered study vaccine reported as being the correct one but is not compatible with the vaccine regimen associated to the treatment number
1080	Vaccine temperature deviation
1090	Expired vaccine administered
1500\$	Subjects who have received only one dose of vaccination
2010	Protocol violation (inclusion/exclusion criteria)
2080	Subjects did not comply with vaccination schedule (DOSE 1 to DOSE 2 = 23-36 (days))

*\$ Attribution of code to a subject requires CRDL confirmation*

*Please note that all the elimcode has to be checked for the subject under schedule 1.*

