## 9. CHANGES FROM PLANNED ANALYSES

Following are the changes in the planned analysis:-

- The naming of the cohort has been changed per cDISC standards.
- Per cDISC standard, the day of first vaccination is now changed from Day 0 to Day 1.
- The study design diagram has been adapted as per cDISC format
- In secondary endpoints, specific safety endpoints for Day 1 up to D366 has been added as follows: -
  - Occurrence of SAEs from study start (Day 1) up to Day 366.
  - Occurrence of RSV-LRTI (AE of specific interest) as from Dose 1 administration up to Day 366.
  - Occurrence of RSV-RTI, RSV-LRTI, severe RSV-LRTI (according to standardized case definitions) as from Dose 1 administration up to Day 366.
- For the immunogenicity analysis, the analysis will be performed on both PPS and ES without any condition on percentage of subjects excluded
- For inclusion of subjects in PPS for analysis of immunogenicity, subjects should have received both the doses and not atleast one dose.

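### The SAP's two-dose rule acts on the whole infant, so the primary (per-protocol) Day 31 summaries drop valid post-Dose 1 samples from infants who later missed Dose 2

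*Protocol*

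**What the plan says.** Protocol 11.5.2 opens with "The ATP cohort for analysis of immunogenicity will be defined by timepoint" and then describes only two sets, one up to Day 60 and one at Day 365. Its dose criterion is "Who received at least one dose of study vaccine". A separate criterion reads "Who complied with the vaccination schedule, as specified in" Table 5, with no time-point qualifier.

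SAP 5.1.2 replaces the dose criterion with "Who received two dose of study vaccine". SAP Section 9 declares the change ("subjects should have received both the doses and not atleast one dose") without giving a reason. SAP 5.2.2.1 implements it as code 1500, "Subjects who have received only one dose of vaccination", in the table of subjects excluded from both the Day 61 and the Day 366 PPS. The code needs confirmation by the clinical lead, but no criterion is given for sparing the Day 31 result. The codes that remove data by visit (SAP 5.2.2.2 and 5.2.2.3) exist only for Visits 9 and 10, so there is no Visit 5 set.

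The post-Dose 1 response is a named secondary endpoint for both humoral and cell-mediated immunity (Protocol 11.2, SAP 4.2). SAP 6.2.1 makes the PPS analysis primary and the Exposed Set analysis complementary. SAP days are protocol days plus one.

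**The concern.** A sample taken before Dose 2 cannot be affected by whether Dose 2 is later given. Requiring Dose 2 for that sample to count conditions a post-Dose 1 summary on a later event. That event is not always unrelated to Dose 1. Under Protocol 6.6.11.2, an abnormal Day 7 blood result that does not return to the acceptable range within the Visit 5 window means no Dose 2, with the infant staying in follow-up. Protocol 7.5 lists further contraindications after which other study procedures may continue. Infants selected by their reaction to Dose 1 can thus leave the primary summary of the response to Dose 1.

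At stake are the Day 31 GMTs/GMCs, fold rises and T-cell frequencies in the primary immunogenicity analysis, in groups that may hold only about 8 infants. The adult study gives a reason to look at this time point: it saw a rise of about 2.4-fold in neutralizing titre after Dose 1, and "No booster effect was evident after Dose 2" (Protocol 1.1.6).

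**Working it through.** No sample size, power or error rate in the documents depends on this rule, so there is no stated figure to reproduce. The check follows one infant through the rules and then gives the scale.

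**Step 1: follow a one-dose infant.**
- The infant receives Dose 1. Blood for immunogenicity is drawn at Visit 5 before any vaccination (Protocol Table 5, footnote g). Dose 2 is not given and the infant stays in the study.
- Protocol 11.5.2: the one-dose criterion is met. The vaccination-schedule criterion may or may not be, so the protocol is unclear.
- SAP 5.1.2 and code 1500: the infant leaves the Day 61 and Day 366 PPS entirely.
- Templates 37, 40, 41 and 42 are PPS tables with PI(D31) rows, so the infant's Day 31 result drops out of them. Template 38 (vaccine response) has no Day 31 row and is unaffected.
- SAP 6.2.1 and Section 9: the Exposed Set analysis is always run, and there the result remains.

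**Step 2: other codes with the same effect.** Code 2080 (Dose 1 to Dose 2 outside 23-36 days) is also a whole-subject exclusion. Code 2090 for the Day 61 set checks the Dose 1 to Visit 5 window (23-36 days) together with the Dose 2 to Visit 9 window (28-35 days). A deviation at Dose 2 or Visit 9 can therefore remove a sound Day 31 result.

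**Step 3: size per infant.** Groups hold about 8 infants at the minimum in Steps 1 and 2, and about 16 otherwise (Protocol Table 1 footnote). The GMT interval is a t-interval on log titres (SAP 11.3.4), so its half-width in log-SD units is t(0.975, n−1)/√n.

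| Group | Infants lost | Share of group | Half-width before → after | Widening |
|---|---|---|---|---|
| 8 | 1 | 1/8 = 12.5% | 0.836 → 0.925 | 10.6% |
| 8 | 2 | 2/8 = 25% | 0.836 → 1.049 | 25.5% |
| 16 | 1 | 1/16 = 6.25% | 0.533 → 0.554 | 3.9% |
| 16 | 2 | 2/16 = 12.5% | 0.533 → 0.577 | 8.4% |

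For comparison, Protocol 11.9 called for a second analysis once more than 10% of a group's infants with results were excluded. One infant of 8, or two of 16, passes that mark.

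**Step 4: how often.** The documents give no rate of missed second doses. With an assumed rate w, the chance that a group loses at least one infant is 1 − (1 − w)^n:

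| Assumed w | n = 8 | n = 16 |
|---|---|---|
| 2% | 15% | 28% |
| 5% | 34% | 56% |
| 10% | 57% | 81% |

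**Step 5: possible bias, illustration only.** If k excluded infants had a fold rise differing two-fold from the others (an assumption without support in the documents), the Day 31 geometric mean ratio would shift by a factor of 2^(k/n). For one infant this is 1.09 with n = 8 and 1.04 with n = 16.

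**The case against.** The strongest reply is that the SAP has already dealt with the matter. The same Section 9 that brings in the two-dose rule also drops the 10% condition, so the Exposed Set analysis always reports these infants. The change is declared. Both immunogenicity objectives (Protocol 2.2) concern responses to two doses, so a per-protocol set of infants who received the full regimen is conventional, and it keeps the Day 31 and Day 61 rows on nearly the same infants. The analyses are within-group and descriptive (SAP 6.2.1, Section 7).

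The route to a missed second dose is also narrow. Day 7 haematology is done only after a platelet decrease of Grade 1 or more on Day 1, and Dose 2 is lost only if the value stays unacceptable through the window. In the related-vector adult studies 7 of 270 (2.6%) met the thrombocytopenia threshold (Protocol 1.3.1). At that illustrative rate, two or more such infants in a group of 8 has probability 1 − 0.974^8 − 8 × 0.026 × 0.974^7, about 1.7%. Infants who leave before Visit 5 have no sample to recover.

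Most of this stands and limits the point. It does not remove it. The endpoints list post-Dose 1 separately from post-Dose 2, both documents say the cohort is defined by time point, and the set that conditions on a later event is the one called primary.

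A reader might infer that the protocol's own line discards data. It does not: the removal comes from the SAP. Read alone, the protocol line has the opposite weakness of admitting one-dose infants to post-Dose 2 rows, though its schedule criterion may exclude them.

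**Conclusion.** The point holds for the PPS. The SAP's two-dose rule removes valid Day 31 results from the primary post-Dose 1 summaries because of an event after the sample, and that event may be related to Dose 1. Each such infant costs 6.25-12.5% of a group and widens the log-scale GMT interval by about 4-11%.

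Stronger readings are not supported:
- Day 31 data are not lost from the trial report, because the Exposed Set analysis always includes them.
- The Day 31 estimates cannot be said to be biased. The number of one-dose infants and any difference in their response are unknown, and the two-fold figure is only an illustration. With an assumed SD of 0.5-0.9 on the natural-log scale, the 95% interval factor is exp(0.836 × SD), about 1.5-2.1, for 8 infants. It is exp(0.533 × SD), about 1.3-1.6, for 16. Shifts of 1.04-1.09 lie well inside both.
- It is tempting to say that Day 31 carries most of the immunogenicity information. That rests on adults aged 18 to 45 and need not carry over to infants.

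No error rate or power is affected. The change is worth making because it is cheap and brings the primary set into line with the endpoint.

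**What to change.** - In SAP 5.1.2, define a separate Visit 5 (Day 31) PPS that requires at least one dose and a valid, in-window sample drawn before Dose 2. Keep two doses as the requirement for the Day 61 and Day 366 rows.
- Move code 1500 out of the whole-subject table in 5.2.2.1 and apply it from Visit 9 onward. Moving it to the existing visit-specific codes is not enough, because these cover only Visits 9 and 10; a Visit 5 value must be added.
- Make code 2080, and the Dose 2 to Visit 9 part of code 2090, leave Day 31 results in place. The Dose 1 to Visit 5 window check should govern the Visit 5 set alone.
- Take the PI(D31) rows of the PPS tables from the Visit 5 set.
- Record the change and its reason in SAP Section 9.

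The cost is SAP wording and one extra analysis-set flag. N will differ slightly between the Day 31 and Day 61 rows, which a footnote can explain. No new data are needed, and no change to the rules for giving or withholding Dose 2 is implied.

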11.6. Derived and transformed data

11.6.1. Demography

For a given subject and a given demographic variable, missing measurements will not be replaced.

11.6.2. Safety

For a given subject and the analysis of solicited AEs during the 7-day follow-up period after vaccination, missing or non-evaluable measurements will not be replaced. Therefore the analysis of the solicited symptoms based on the TVC will include only vaccinated subjects with documented safety data (i.e. symptom screen completed).

For analysis of unsolicited AEs, SAEs and for the analysis of concomitant medications, all vaccinated subjects will be considered. Subjects who did not report an event or concomitant medication will be considered as subjects without the event or the concomitant medication respectively.

11.6.3. Immunogenicity

Any missing or non-evaluable immunogenicity measurement will not be replaced:

- For the within-group assessment, the descriptive analysis performed for each assay at each timepoint will exclude subjects with a missing or non-evaluable measurement. Kinetics will be plotted on subjects with results available at all timepoints.

The geometric mean titers/concentrations (GMTs/GMCs) will be computed by taking the anti-logarithm of the arithmetic mean of the log₁₀ transformed titers/concentrations.

A seronegative subject will be defined as a subject whose antibody titers/concentrations is below the cut-off value of the assay. A seropositive subject is a subject whose antibody titers/concentrations is greater than or equal to the cut-off value of the assay.

Vaccine response in terms of RSV neutralizing antibodies will be defined in the statistical analysis plan.

The description of the handling of data below the lower limit of quantification for GMC calculation and fold increase will be described in the statistical analysis plan.

11.6.4. RTI and LRTI

For the analysis of RTI and LRTI, all cases will be definitively classified as either RTI, LRTI or severe LRTI according to standardized case definitions (see [Table 4](#)) based on the available WHO case definitions, and the association to RSV infection will be assessed by quantitative PCR as primary analysis.

All confirmed LRTI will also be investigated for a panel of respiratory viruses (multiplex PCR; refer to [Table 10](#)), as a supplementary analysis of the occurrence of RSV-LRTI diagnosed upon the multiplex PCR.

For the analysis of RTI episode, a new RTI episode will be defined as any occurrence of cough, runny nose, blocked nose or difficulty breathing with an interval of at least 7 symptom free days since the last episode of RTI that was diagnosed (refer to [Section 4.2](#) for the definition of start and end dates of RTI episode).

11.7. Analysis of demographics

The analysis of demographics will be performed on the TVC and on the ATP cohort for immunogenicity.

Demographic characteristics (age at vaccination in months, gender, race), weight, height or length, and vital signs, and cohort description will be summarized by group using descriptive statistics:

- Frequency tables will be generated for categorical variable such as race.
- Mean, median, standard error and range will be provided for continuous data such as age.

The distribution of subjects will be tabulated as a whole and per group.

Withdrawal status will be summarized by group using descriptive statistics:

- The number of subjects enrolled into the study as well as the number of subjects excluded from ATP analyses will be tabulated.
- The numbers of withdrawn subjects will be tabulated according to the reason for withdrawal.

11.8. Analysis of safety

11.8.1. Within groups assessment

The analysis will be performed on the TVC.

The percentage of subjects with at least one **local AE** (solicited and unsolicited), with at least one **general AE** (solicited and unsolicited) and with any AE during the 7-day or 30-day follow-up period will be tabulated with exact 95% CI after each vaccine dose and overall (**Amended 10 December 2017**). The percentage of doses followed by at least one local AE (solicited and unsolicited), by at least one general AE (solicited and unsolicited) and by any AE during the 7-day or 30-day follow-up period will be tabulated, overall vaccination course, with exact 95% CI. The same computations will be done for Grade 3 AEs, for any AEs considered related to vaccination and for any Grade 3 AEs considered related to vaccination.

The percentage of subjects reporting each individual **solicited local AE** (any grade, Grade 2, Grade 3, resulting in a medically attended visit) and **solicited general AE** (any grade, Grade 2, Grade 3, any related, Grade 2 related, Grade 3 related, resulting in medically attended visit) during the 7-day follow-up period (Day 0-6) will be tabulated for each group after each vaccine dose and overall. Similarly, the percentage of doses followed by each individual solicited local and general AE and their sub-categories, will be tabulated, overall vaccination course, with exact 95% CI.

For fever, the number and percentage of subjects reporting fever by half degree (°C) cumulative increments during the 7-day follow-up period (Day 0-6) will be tabulated for each group after each vaccine dose and overall. Similar tabulations will be performed for any fever with a causal relationship to vaccination, Grade 3 (> 39.5°C) causally related fever and for any fever resulting in a medically attended visit. In addition, the prevalence of any and Grade 3 fever will be presented graphically over time after vaccination.

For each group and for each **hematology and biochemistry** parameter:

- The percentage of subjects having hematology and biochemistry results below or above the local laboratory normal ranges will be tabulated by timepoint.

The maximum grading from Screening up to Visit 9 (Day 60) will be tabulated (Refer to [Appendix C](#)).

The percentage of subjects with **unsolicited** AEs within 30 days (Day 0-29) after each vaccine dose (overall doses) with its exact 95% CI will be tabulated by group and by MedDRA preferred term. Similar tabulation will be done for Grade 3 unsolicited AEs, for any causally related unsolicited AEs, for Grade 3 causally related unsolicited AEs and for unsolicited AEs resulting in a medically attended visit. The verbatim reports of unsolicited AEs will be reviewed by a physician and the signs and AEs will be coded according to the MedDRA Dictionary for Adverse Reaction Terminology. Every verbatim term will be matched with the appropriate Preferred Term.

SAEs reported throughout the study and AE of specific interest will be described in detail.

The percentage of subjects using **concomitant medication** (any medication, any antipyretic and any antipyretic taken prophylactically, respectively) during the 7-day follow-up period (Day 0-6) and during the 30-day follow-up period (Day 0-29) will be summarized by group after each vaccine dose and overall.

